7.1.3.4 Aberrant Behavior Checklist – Community (ABC-C)

The ABC-C is a 58-item questionnaire designed to assess problematic behavior at home, in educational and work setting, and in residential and community-based facilities. The item scores range from 0="not at all a problem" to 3="the problem is severe in degree". The items are partitioned into 5 domains:

1. Irritability (items 2, 4, 8, 10, 14, 19, 25, 29, 34, 36, 41, 47, 50, 52, 57)
2. Social withdrawal (items 3, 5, 12, 16, 20, 23, 26, 30, 32, 37, 40, 42, 43, 53, 55, 58)
3. Stereotypy behavior (items 6, 11, 17, 27, 35, 45, 49)
4. Hyperactivity (items 1, 7, 13, 15, 18, 21, 24, 28, 31, 38, 39, 44, 48, 51, 54, 56)
5. Inappropriate speech (items 9, 22, 33, 46)

The domain subtotals and the total of all the items will be summarized with descriptive statistics of the baseline and post-baseline values and the arithmetic changes from baseline. Difference in mean scores between two treatment groups will be provided along with 95% confidence intervals.

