IND	Investigational New Drug
IRB	institutional review board
ITT	Intent-to-Treat Population
IWRS	interactive web response system
LAR	legally authorized representative
LGS	Lennox Gastaut syndrome

Term	Definition
MedDRA	Medical Dictionary for Regulatory Activities
MRI	magnetic resonance imaging
MTD	Maximum Tolerated Dose
OL	open-label
PBO	Placebo
PCDH19	protocadherin 19
PedsQL-FIM	Pediatric Quality of Life Inventory – Family Impact Module
PI	principal investigator
PK	Pharmacokinetic
QI-Disability	Quality of Life Inventory-Disability
RR	respiratory rate
SAE	serious adverse event
SAP	statistical analysis plan
SGOT	serum glutamic oxaloacetic transaminase
SGPT	serum glutamic pyruvic transaminase
SIF/DRF	Seizure Identification and Diagnostic Review Form
SOC	standard of care
TEAE	Treatment-emergent adverse event
THC	tetrahydrocannabinol
TID	3 times daily
ULN	upper limit of normal
UK	United Kingdom
US	United States
VNS	Vagus nerve stimulator
VUS	variant of unknown significance

STUDY SYNOPSIS

Protocol number: 1042-PCDH19-3002	Drug: ganaxolone
Title of the study: A double-blind, randomized, placebo-controlled trial of adjunctive ganaxolone treatment in female children with protocadherin 19 (PCDH19)-related epilepsy followed by long-term open-label treatment	
Number of subjects (total and for each treatment arm): A sufficient number of eligible PCDH19 subjects will be screened and enrolled, with a 1:1 randomization to either ganaxolone (GNX) or placebo (PBO). As study enrollment was discontinued early (as of 01July2020) due to administrative reasons, the total number of the randomized patients is expected to be approximately 25 subjects resulting in approximately 15 randomized biomarker-positive subjects.	
Investigators: Multicenter study	
Sites and Regions: Global, multicenter study to be conducted at approximately 11 sites	
Study period (planned): March 2019 to June 2022	Clinical phase: 2
Objectives:	
Primary: To assess the efficacy of GNX compared with PBO as adjunctive therapy for the treatment of primary seizure types in children with genetically confirmed PCDH19-related epilepsy during the 17-week double-blind (DB) phase.	
Secondary:	

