7.4.5. Aberrant Behavior Checklist – Community (ABC-C)

The ABC-C is a questionnaire designed to assess problematic behavior at home, in educational and work setting, and in residential and community-based facilities.

The ABC-C will be assessed as follows: in the DB phase at Visit 2 (baseline/randomization) and Visit 5 (Week 17; also Final DB Visit/First OL Visit in OL phase); in the OL phase at Visit 7 (Week 36) and Visit 9 (Week 68) and thereafter every 16 weeks for the duration of this phase; and at the Final OL Visit.

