1.3 STUDY DESIGN

1.3.1 General Study Design and Plan

This is a global, biomarker-stratified, DB, randomized, PBO-controlled trial of adjunctive GNX treatment of primary seizures in female children with a confirmed pathogenic or likely pathogenic PCDH19 mutation. The trial consists of a prospective baseline period of 8 to 12 weeks in duration to collect seizure data, followed by a 17-week DB treatment phase, which is then followed by a long-term OL phase (Figure 1). An interactive web response system (IWRS) will be used to randomize subjects, dispense drug, track treatment, and maintain the blind throughout the duration of the study.

[figure not shown]
During the screening visit, each subject's allopregnanolone sulfate (Allo-S) biomarker level will be assessed via a blood draw and subsequent analytical quantification. Each subject will then be assigned to 1 of 2 groups: biomarker-positive or biomarker-negative. A subject will be considered biomarker-positive if the baseline Allo-S level is less than or equal to 2500 pg/mL (Pinna Lab method or similar). A subject with a baseline Allo-S level greater than 2500 pg/mL will be classified as biomarker-negative. The biomarker group assignment will remain blinded until database unblinding. Based on the 11-subject

OL study, it is estimated that approximately 65% of subjects will be biomarker-positive.

The DB phase includes 4 weeks of investigational product (IP) titration followed by 13 weeks of dose maintenance. After meeting the eligibility criteria, approximately 25 children aged 1 to 17 years (inclusive) with PCDH19-related epilepsy will be randomly assigned to receive GNX or PBO (1:1 ratio within each biomarker stratum) for 17 weeks in addition to their standard anti-seizure treatment. Subjects will be titrated to 63 mg/kg/day (max 1800 mg/day) over 4 weeks and then maintained at that dose for another 13 weeks. Subjects who are not able to tolerate 63 mg/kg/day (or 1800 mg/day maximum) may be maintained on a lower dose. A minimum dose of 33 mg/kg/day or 900 mg/day is generally required following the DB escalation period, unless a lower dose is agreed to with the sponsor due to the tolerability such as somnolence. At each visit, dosing will be reviewed and adjusted as needed based on subject's current weight.

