7 EFFICACY ANALYSES

In addition to the descriptive statistics mentioned in Section 2.1, the baseline, post-baseline, and relevant changes from baseline for the seizure endpoints will also be summarized. Wilcoxon rank-sum tests will be used to compare differences in percent change from baseline between the two treatment groups.

Fisher's exact test will be used to compare the percentage of subjects achieving notable reductions, e.g. $\geq 25\%$ reduction, $\geq 50\%$ reduction, etc., in seizure rates between the two treatment groups.

The baseline, post-baseline, and changes from baseline for the other non-categorical endpoints will be summarized descriptively with 95% confidence intervals for the means and differences in means between the treatment groups.

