7.1.3.3 Behavior Rating Inventory of Executive Function (BRIEF, preschool version BRIEF-P)

The BRIEF is an 86-item questionnaire designed to assess executive function behaviors in the school and home environments in individuals 5-18 years of age. The preschool version (BRIEF-P) is a 63-item modified form and will be administered to individuals 2-5 years of age. The BRIEF version to be administered will be based on the subject's age at Screening. The same version of the BRIEF will be administered during the entire study regardless of the subject's age at the time of post-screening assessment. The questionnaire is completed by the parents/caregiver/ legally authorized representative (LAR).

The BRIEF items are partitioned to create 8 component scores:

- Inhibit
- Shift
- Emotional Control
- Initiate
- Working Memory
- Plan/Organize
- Organization of Materials
- Monitor

The first three components are summed to create a Behavioral Regulation Index (BRI), and the remaining five components are summed to create a Metacognition Index (MI). The BRI and MI are then summed to create a Global Executive Composite (GEC).

The BRIEF-P items are partitioned to create 5 component scores:

- Inhibit
- Shift
- Emotional Control
- Working Memory
- Plan/Organize Scales

The Inhibit and Emotional Control components are summed to create an Inhibitory Self-Control Index (ISCI), the Shift and Emotional Control components are summed to create a Flexibility Index (FI), the Working Memory and Plan/Organize components are summed to create an Emergent Metacognition Index (EMI), and all five components are summed to create a Global Executive Composite (GEC).

All component scores, index scores, and composite scores will be descriptively summarized. Both baseline, post-baseline, and change from baseline will be summarized. These scores will also be listed. Statistical comparison between treatment groups will not be performed.

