7.1.3.5 Children's Sleep Habit Questionnaire (CSHQ)

The CSHQ is a psychological questionnaire designed to measure sleep behaviors in children and adolescents and is filled out by the parent/caregiver/LAR. An abbreviated version contains 33 items.

The first 31 items are scored as 1 = Rarely (0-1 times per week), 2 = Sometimes (2-4 times per week), or 3 = Usually (5 - 7 times per week). Item 32 (Watching TV) and 33 (Riding in car) ask how sleepy the child has appeared during those activities (1 = Not sleepy, 2 = Very sleepy, or 3 = Falls asleep). The questionnaire includes 2 other quantitative questions:

- Child's usual amount of sleep each day
- Number of minutes a night waking usually lasts

The 33 items are partitioned into 8 domains:

1. Bedtime resistance (items 1, 3, 4, 5, 6, 8)
2. Sleep onset delay (item 2)
3. Sleep duration (items 9, 10, 11)
4. Sleep anxiety (items 5, 7, 8, 21)
5. Night wakings (items 16, 24, 25)
6. Parasomnias (items 12-15, 17, 22, 23)
7. Sleep disordered breathing (items 18, 19, 20)
8. Daytime sleepiness (items 26-33)

For scoring, first, items 1, 2, 3, 10, 11, and 26 are reversed (4-score). The item scores are then summed within each domain. The domain subtotals, the total of the 33 items, and the 2 other quantitative questions will be summarized with descriptive statistics of the baseline and post-baseline values and the arithmetic changes from baseline. Differences in mean scores between two treatment groups will be provided along with 95% confidence intervals.

The usual amount of sleep each day will be summarized in hours.

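### For ABC-C and CSHQ the SAP plans only unadjusted between-arm differences; an overall estimate adjusted for the Visit 2 score and biomarker stratum would be a cheap, modest gain in precision

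*SAP*

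**What the plan says.** SAP 7.1.3.4 (ABC-C) says: "Difference in mean scores between two treatment groups will be provided along with 95% confidence intervals". SAP 7.1.3.5 (CSHQ) says nearly the same: "Differences in mean scores between two treatment groups will be provided along with 95% confidence intervals". Neither names a model or a covariate.

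SAP Section 7 sets the general rule: "The baseline, post-baseline, and changes from baseline for the other non-categorical endpoints will be summarized descriptively", with 95% confidence intervals for the means and for the differences in means between arms. The baseline difference is therefore reported too.

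In the double-blind phase the ABC-C is assessed "in the DB phase at Visit 2 (baseline/randomization) and Visit 5" (Protocol 7.4.5), and Protocol 7.4.3 gives the same schedule for CSHQ. Week 17 is thus the only post-baseline double-blind value.

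On which contrast matters, the secondary objective (Protocol 2.2.2, SAP 1.1.2) speaks of behavioural changes, and SAP 7.1.3 has secondary endpoints compared relative to baseline unless stated otherwise.

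On stratum, SAP 1.3.1 randomises 1:1 within biomarker stratum. SAP 7.1.3 reports secondary results for all subjects and separately by stratum, with no combined estimate that accounts for stratum.

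On size, the protocol synopsis says "the total number of the randomized patients is expected to be approximately 25 subjects resulting in approximately 15 randomized biomarker-positive subjects".

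**The concern.** In a trial of about 25 children the arms can differ by chance on a behavioural score at Visit 2. The unadjusted Week 17 difference carries whatever part of that imbalance persists. The unadjusted change subtracts all of the baseline score, which over-corrects when the correlation between visits is below 1. Adjusting for the Visit 2 score uses data already in hand and avoids having to guess that correlation. Adjusting for stratum makes the overall analysis follow the way subjects were allocated.

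At stake is the width of descriptive intervals that will already be wide, and how far they are moved by chance imbalance. No test, alpha or decision rule depends on it.

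**Working it through.** The documents give no SD, power or correlation for these scales, so there is no plan figure to reproduce. Results are in units of the score SD, assumed equal at both visits.

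**Inputs**
- N = 25 (protocol synopsis), split 12 v 13 (assumed).
- ρ, the Visit 2 to Week 17 correlation: assumed, 0.3 to 0.8.
- t quantiles (97.5%): 2.0687 on 23 df (unadjusted) and 2.0796 on 21 df (ANCOVA with two covariates). The ratio is 1.0053.

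**Step 1: chance baseline difference.** SE = √(1/12 + 1/13) = 0.40 SD. The probability that it exceeds 0.5 SD in either direction is 2[1 − Φ(0.5/0.400)] = 0.21. The unadjusted Week 17 and change estimates differ by exactly this baseline difference.

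**Step 2: relative variances.** Week 17 score: 1. Change: 2(1 − ρ). ANCOVA: (1 − ρ²) × [1 + 2/(25 − 2 − 3)] = 1.10(1 − ρ²). The factor 1.10 is the expected price of estimating two covariate effects, with stratum given no prognostic value.

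**Step 3: ratio of CI widths, ANCOVA to unadjusted.**
- Against change: √[1.10(1 + ρ)/2] × 1.0053
- Against Week 17: √[1.10(1 − ρ²)] × 1.0053

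| ρ | Against change | Narrower by | Against Week 17 | Narrower by |
|---|---|---|---|---|
| 0.3 | 0.850 | 15% | 1.006 | −1% (wider) |
| 0.5 | 0.913 | 9% | 0.913 | 9% |
| 0.7 | 0.972 | 3% | 0.753 | 25% |
| 0.8 | 1.000 | 0% | 0.633 | 37% |

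**Step 4: simulation check.** Bivariate normal scores, positive/negative counts of 7/5 in one arm and 8/5 in the other, stratum not prognostic. Mean 95% CI half-widths in SD:

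| ρ | Week 17 | Change | ANCOVA with stratum |
|---|---|---|---|
| 0.3 | 0.82 | 0.97 | 0.80 |
| 0.5 | 0.82 | 0.82 | 0.73 |
| 0.7 | 0.82 | 0.63 | 0.60 |
| 0.8 | 0.82 | 0.52 | 0.51 |

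ANCOVA does slightly better here than by formula, because stratified allocation keeps the stratum term nearly orthogonal to treatment.

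**Step 5: cost of the stratum term if it predicts nothing.** Added half-width is 0.001 to 0.003 SD at 7/5 v 8/5, 0.006 to 0.010 SD at 8/4 v 7/6, and 0.025 to 0.038 SD at 9/3 v 6/7.

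**Step 6: within strata.** Simulated ratios of baseline-only ANCOVA to change, at ρ = 0.5, 0.7 and 0.8, are 0.95, 1.01 and 1.04 for 5 v 5 (about 10 biomarker-negative). They are 0.91, 0.97 and 1.00 for 7 v 8 (about 15 biomarker-positive). There is little or nothing to gain at these sizes.

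**The case against.** The strongest reply is that this is a preference and not an error. The scales have no test and no alpha: SAP 7.1 plans significance tests for the primary endpoint, and Fisher's test covers responder rates. Section 7 reports the baseline difference with its interval, so imbalance will be visible. For CSHQ the protocol itself planned only descriptive statistics (9.13.1.3.2.3). Against change, the contrast the SAP leans towards, the gain falls to zero at ρ = 0.8. The simulation uses normal data, whereas the real scores are bounded sums of ordinal items. No document says that Allo-S predicts behaviour or sleep scores.

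Most of this stands. It limits the point to an optional improvement and keeps the estimate descriptive. It does not remove the case for adjustment: the baseline score is already collected, ρ is unknown in advance, and over this range ANCOVA about matches or beats the better unadjusted contrast. The stratum term has no demonstrated precision gain and rests only on matching the randomisation.

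Three stronger readings are tempting and unsupported:
- **That the SAP leaves the contrast of interest entirely open.** It does not use the word principal, but the objective and SAP 7.1.3 both point to change. The phrase in 7.1.3 is seizure-diary language, so the indication is strong without being conclusive.
- **That the unadjusted differences are biased.** Under randomisation they are not.
- **That SAP 7.1.3.3 contradicts Section 7 for BRIEF, where it says "Statistical comparison between treatment groups will not be performed".** That is a specific rule, placed where the next two subsections restate the interval sentence, and SAP 7.1.3 allows exceptions. A programmer would follow it.

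**Conclusion.** The point holds as a low-cost improvement of minor importance. For ABC-C and CSHQ the planned overall estimates leave the Visit 2 score and the randomisation stratum unused. The expected benefit against change runs from about 15% narrower at ρ = 0.3 to none at 0.8. Against the Week 17 score it runs from 1% wider to 37% narrower. These sizes rest on 12 v 13 subjects with both scores present, equal SDs at the two visits, approximate normality and an assumed ρ. Missing Week 17 scores would reduce N and raise the relative cost of two covariates. The case does not extend to the by-stratum results.

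**What to change.** In SAP 7.1.3.4 and 7.1.3.5, for the ABC-C and CSHQ total and multi-item domain scores in the overall ITT population, make the main estimate the treatment difference with 95% CI from an ANCOVA of the Week 17 score on treatment, Visit 2 score and biomarker stratum. Label it descriptive. Keep the unadjusted difference in change as supportive, along with the planned summaries. Use the unadjusted difference in change for the by-stratum results, the single-item CSHQ domain (sleep onset delay) and the two CSHQ quantitative questions.

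The cost is wording and standard code before the double-blind database is locked, plus two model degrees of freedom (t from 2.07 to 2.08). If stratum is not prognostic, its term adds about 0.00 to 0.01 SD of half-width with near-balanced strata. It adds 0.03 to 0.04 SD if they are very uneven, which stratified randomisation makes unlikely. No data collection, p-value or alpha changes. BRIEF needs at most a cross-reference in SAP Section 7 noting the exception in 7.1.3.3.

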7.1.3.5 Children's Sleep Habit Questionnaire (CSHQ)

The CSHQ is a psychological questionnaire designed to measure sleep behaviors in children and adolescents and is filled out by the parent/caregiver/LAR. An abbreviated version contains 33 items.

The first 31 items are scored as 1 = Rarely (0-1 times per week), 2 = Sometimes (2-4 times per week), or 3 = Usually (5 - 7 times per week). Item 32 (Watching TV) and 33 (Riding in car) ask how sleepy the child has appeared during those activities (1 = Not sleepy, 2 = Very sleepy, or 3 = Falls asleep). The questionnaire includes 2 other quantitative questions:

- Child's usual amount of sleep each day
- Number of minutes a night waking usually lasts

The 33 items are partitioned into 8 domains:

1. Bedtime resistance (items 1, 3, 4, 5, 6, 8)
2. Sleep onset delay (item 2)
3. Sleep duration (items 9, 10, 11)
4. Sleep anxiety (items 5, 7, 8, 21)
5. Night wakings (items 16, 24, 25)
6. Parasomnias (items 12-15, 17, 22, 23)
7. Sleep disordered breathing (items 18, 19, 20)
8. Daytime sleepiness (items 26-33)

For scoring, first, items 1, 2, 3, 10, 11, and 26 are reversed (4-score). The item scores are then summed within each domain. The domain subtotals, the total of the 33 items, and the 2 other quantitative questions will be summarized with descriptive statistics of the baseline and post-baseline values and the arithmetic changes from baseline. Differences in mean scores between two treatment groups will be provided along with 95% confidence intervals.

The usual amount of sleep each day will be summarized in hours.

7.1.4 Exploratory Endpoints

A large rectangular area of the page is completely blacked out, indicating that the content has been redacted for confidentiality.

Marinus Pharmaceuticals, Inc.

Study 1042-PCDH19-3002

Statistical Analysis Plan,

Amendment 1

01 March 2021

Marinus Pharmaceuticals, Inc.

Study 1042-PCDH19-3002

Statistical Analysis Plan,

Amendment 1

01 March 2021

7.1.5 Subgroup Analyses

Other than the within-stratum analyses, no subgroup analyses are planned at this time.

7.1.6 Sensitivity Analyses

Two sensitivity analyses of the primary efficacy endpoint of change in 28-day frequency of the primary (i.e., all countable motor) seizure types will be performed:

Intermittent (random/sporadic) missing data during the 17-week DB phase and any missing data during the baseline phase will be assumed missing completely at random and the collected data will be used to calculate the 28-day seizure frequencies. For early drug termination prior to the end of the 17-week DB phase, caregivers will be instructed to continue to provide daily seizure records until the end of the 17-week DB phase (hence further preventing missingness).

In the first sensitivity analysis, the following imputation approach will be used for the primary outcome measure when a subject stops recording measurements permanently (anticipated to be zero or minimal in occurrence) prior to the end of the 17-week DB phase. For days with missing seizure count data, the corresponding median PBO data will be imputed (irrespective of treatment arm), within each stratum, as follows:

- Compute the median 28-day seizure frequency in the PBO arm based on all available PBO measurements during the 17-week DB treatment phase. Label that

‘X’ and define ‘A’ to be ‘X’/28, (i.e., the daily average on placebo during the 17-week during the DB phase).

- For any days (whether they be in the PBO or GNX arm) that occur AFTER a subject has become lost to follow up, impute ‘A’ on that day.

The second sensitivity analysis will explore the possibility that subjects who stop recording their seizure counts tend to have higher seizure counts than the other subjects. The imputation method described above will be modified to use the median of the 5 highest counts, rather than the median count, among the PBO subjects with data.

7.1.7 Protections for Multiplicity

As explained in Section 7.1.2, analyses of the 28-day seizure frequency will be conducted in the following sequence:

- The primary analysis will be conducted using all subjects in the ITT population.
- If nominal statistical significance is achieved in the ITT population, the primary analysis will be similarly conducted in the biomarker-positive stratum of the ITT population as a secondary endpoint (Section 7.1.3).
- In addition, as an exploratory analysis, efficacy will be assessed in the biomarker-negative stratum. (Section 7.1.4.1)

7.2 OPEN LABEL EXTENSION

All of the analyses for the DB phase will be repeated for the OL phase, with the following differences:

- All results will only be summarized descriptively.
- The results will be presented overall and classified according to the DB treatment received by the subjects
- The post-baseline seizure endpoints will be derived based on the first full day of OL treatment (one day after OL start).
- No sensitivity analyses will be performed.
- Analyses of seizure frequencies during titration and maintenance phases are only applicable to the DB phase and will not be included in the OL phase analyses.
- The time points for the efficacy, exploratory, and quality of life endpoints will be after 19 weeks, 51 weeks, and every 16 weeks thereafter of open-label treatment relative to the prospective baseline phase.
- The differences between the DB treatment groups in the percent changes from baseline of the 28-day seizure frequencies will not be tested for statistical significance.

- No PP analyses will be performed.

